7.4.5.4 Corneal and conjunctival staining with lissamine green

After the revision with fluorescein, a drop of saline solution will be applied to the tip of the green lissamine strip, allowing it to sit on the strip for 5 seconds to elute the dye. A drop of the strip is instilled at the bottom of the temporal sac, while the patient looks upwards, without damaging the conjunctiva. The patient may be asked to blink repeatedly to prevent accumulations in the conjunctival folds. The examination should be done between 1 and 4 minutes after instillation through a neutral density filter or with the red-free filter. It will be graded according to the Oxford scale. [50]

The PI will record in the file and the eCRF the grade awarded for fluorescein staining of DO and OS, respectively.

Management as AE: corneal stains that are equal to or greater than grade III will be considered as AEs.

7.4.5.5 Conjunctival hyperemia

Conjunctival hyperemia is defined as the simplest reaction of the conjunctiva to a stimulus, with a red appearance secondary to vasodilation of the conjunctival vessels of variable intensity. You will graduate using the Efron scale (See 16.3). [51]

Management as AE: conjunctival hyperemia classified as grade 3 or higher will be considered as AE.

7.4.5.6 Chemosis

It is defined as conjunctival edema, the result of an inflammatory reaction. It is qualified as present or absent. The evaluator will use a narrow beam of light at 60° and will measure whether the conjunctiva separates from the sclera by $\geq 1/3$ of the total eyelid opening or if it exceeds the gray line. [52]

Management as an AE: your presence will be considered as an AE.

7.4.5.7 Adverse events

As defined in section 8.1.1, an AE is any unfavorable medical occurrence in a subject to whom an IP is administered, regardless of causal attribution.

Management of AEs will be performed as described in the Adverse Events section.

The PI will record in the corresponding section of the eCRF the AEs that the study subjects present, in addition to referring them to the clinical file.

For an adequate evaluation of AEs, in addition to directed questioning, it is necessary to perform the Comprehensive Ophthalmological Evaluation at each visit, which consists of: ophthalmological examination of the eyelids and adnexa; anterior and posterior segment that is performed in a routine ophthalmological check-up, whose procedures are not specifically included in the study variables. Posterior pole evaluation can be with direct or indirect ophthalmoscopy, with or without pharmacological mydriasis, at the discretion of the PI. An assessment of the fundus will be carried out in search of abnormalities that alter the result of the study. IOP will be measured in this evaluation, with the instrument chosen by the PI, it should be measured after the evaluation of stains. The result of the assessment will be recorded in the clinical file. In the eCRF, only the findings that are considered so by the PI will be reported as AEs.

The AEs expected for the use of PIs are: blurred vision, burning, eye irritation, foreign body sensation, and sticky eyelash sensation. They are expected to be transient, lasting no more than 30 seconds after IP instillation, and to be of mild intensity.

7.4.5.8 Better corrected visual acuity

Visual acuity (VA) is a test of visual function. Spatial VA is the ability to distinguish separate elements of an object and identify them as a whole. It is quantified as the minimum angle of separation (located at the nodal point of the eye) between two objects that allows them to be perceived as separate objects.

Snellen's notation is described as the distance at which the test is performed, divided by the distance at which the letter is vertically equivalent to 5 arc minutes. Thus, at 6 meters a letter 6/6 (20/20) is equivalent to 5 minutes of arc, a letter 6/12 (20/40) is equivalent to 10 minutes, and a letter 6/60 (20/200) is equivalent to 50 minutes. The Snellen fraction can also be expressed as a decimal (i.e., $20/20 = 1$ and $20/40 = 0.5$). [53]

VA will be evaluated at baseline, without refractive correction with the Snellen chart. It will be located in a place with adequate lighting, natural or artificial, and at a distance of 3m from the subject to be evaluated. The visual acuity of each eye will be taken, starting with the right eye (OD) asking the subject to keep both eyes open and using an occluder to cover the left eye (OS); the subject will read aloud the lines that the evaluator points out, the line of smaller letters that he can see will be noted by the evaluator in fraction as the VA of OD in the clinical record. The OS is proceeded with the same method.

Subsequently, the subject's objective and subjective refractive correction will be performed. The result of the subjective refraction will be reported as CVMA, it will be noted in fraction in the clinical record and in the eCRF it will be noted in decimal. By definition, BCVA cannot be inferior to VA.

Management as AE: A decrease of more than 2 lines on the Snellen card must be reported and handled as AE.

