Safety primary outcome variable:

- Incidence of AEs (ET: days 15 and 31).

[figure not shown]
Safety Secondary Outcome Variable:

- Changes in the BCVA (ET: day 15 and 31).
- Changes in intraocular pressure (IOP) (ET: day 15 and 31).

Statistical methodology

The Kolmogorov-Smirnov and Shapiro Wilk tests will be performed, as appropriate, to know if the distribution presents normality in the results obtained in each study group. The data will be expressed with measures of central tendency: mean and standard deviation for the quantitative variables. Qualitative variables will be presented in frequencies and percentages. The statistical analysis will be performed by means of the Analysis of Variance Test (ANOVA) for the quantitative variables for the difference between the groups. The difference between the qualitative variables will be analyzed by means of X² (Chi-square) or Fisher's exact. A 95% CI will be considered for the non-inferiority criteria based on the objectives of the study, an alpha (α) will be considered significant ≤ 0.05

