7.4.4 Secondary outcome of safety

- Changes in the BCVA (ET: day 15 and 31).

- Changes in IOP (ET: day 15 and 31).

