7.4.5 Definition of variables, methods and scales to be used for measurement

Variable	Type of variable	Unit (symbol)	Method of measurement	Normal value	Evaluation time	Test statistics
Primary outcome of efficacy						
OSDI	Quantitative discrete	Score	Questionnaire	< 13	BV and FV	ANOVA Student's t test*
Secondary outcome of efficacy						
TFRT with fluorescein	Quantitative continuous	Second(s)	Direct observation with slit lamp and cobalt blue filter	> 10s	BV, V1 and FV	ANOVA Student's t test*
Corneal and conjunctival staining with lissamine green	Categorical ordinal	Degrees	Direct observation with slit lamp, evaluated with Oxford's scale	0	BV, V1 and FV	Pearson's χ^2 or Fisher's exact test. McNemar's test*
Corneal and conjunctival staining with fluorescein	Categorical ordinal	Degrees	Direct observation with slit lamp, evaluated with Oxford's scale	0	BV, V1 and FV	Pearson's χ^2 or Fisher's exact test. McNemar's test*
Conjunctival hyperemia	Categorical ordinal	Grades (Efron)	Direct observation with slit lamp, evaluated with Efron's scale	0	BV, V1 and FV	Pearson's χ^2 or Fisher's exact test. McNemar's test*
Chemosis	Categorical nominal	Present/absent	Observation	Absent	BV, V1 and FV	Pearson's χ^2 or Fisher's exact test. McNemar's test*
Primary outcome of safety						
AE	Quantitative discrete	Number of Cases (N)	Count	0	BV, V1 and FV	ANOVA
AE(bis)	Categorical nominal	Present/absent (-)	Observation	Absent	BV, V1 and FV	Pearson's χ^2 or Fisher's exact test.
BCVA	Quantitative discrete	Fraction (-)	Snellen chart	1	BV, V1 and FV	ANOVA Student's t test*
IOP	Quantitative discrete	Number	Tonometry	≥ 10 and ≤ 21	V1 and FV	ANOVA Student's t test*

OSDI, ocular surface disease index; TFRT, tear film rupture time; AEs, adverse events; BCVA, better corrected visual acuity; IOP, intraocular pressure; ANOVA, Analysis of Variance; χ^2, Chi-square. *When applicable.
						

Table 3. Operational definition of variables

The variables, method, and scales for their measurement are described in detail below. They are in order according to Table 3.

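### BCVA change is averaged and tested as a Snellen decimal, so each eye's change is weighted by its baseline acuity; convert to logMAR first

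*Combined protocol and SAP*

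**What the plan says.** BCVA change at days 15 and 31 is a secondary safety outcome (section 7.4.4). Section 7.4.5.8 has it read on a Snellen chart and written as a fraction in the clinical record, while "in the eCRF it will be noted in decimal". The same section explains the scale through letter size: 20/20 is 5 minutes of arc, and "a letter 6/12 (20/40) is equivalent to 10 minutes, and a letter 6/60 (20/200) is equivalent to 50 minutes".

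Table 3 (section 7.4.5) classes BCVA as a discrete quantitative variable, with the fraction as unit and 1 as normal value, and lists "ANOVA Student's t test" for it. The synopsis gives "mean and standard deviation for the quantitative variables" and ANOVA for differences between groups; section 10.1.2 is similar. Nothing in the plan converts acuity to logMAR or another log scale before analysis.

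The adverse event rule for the same variable works in chart lines: "A decrease of more than 2 lines on the Snellen card must be reported and handled as AE".

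**The concern.** A mean change can be interpreted if a unit of change means the same for every eye. On the decimal scale it does not. The same proportional enlargement of the smallest readable letter is a large decimal change in an eye that starts well and a small one in an eye that starts poorly. The planned mean therefore mixes how much acuity was lost with where the eyes began, and eyes with good acuity carry most of the weight. A spread of baseline acuity also adds variation to the changes, which costs power.

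At stake is the readability, and to some extent the sensitivity, of one secondary safety comparison across the three dosing groups. The mean change also cannot readily be set against the protocol's own line-based threshold.

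**Working it through.** **The plan's own figures.** Decimal = 20/denominator and letter angle = 5/decimal.

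- 20/20: decimal 1.0, angle 5 minutes
- 20/40: decimal 0.5, angle 10 minutes
- 20/200: decimal 0.1, angle 50 minutes

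These reproduce section 7.4.5.8, so the decimal is the reciprocal of the visual angle (up to the constant 5).

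**Effect of a given loss.** Let an eye start at decimal d and lose L log10 units. It ends at d × 10^(−L), so:

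- change in decimal = d × (1 − 10^(−L)), proportional to d
- change in −log10(decimal) = L, whatever d is

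**One line, if lines are equal 0.1-log steps (assumption).** 1 − 10^(−0.1) = 0.2057.

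| Start | One-line loss, decimal | 20/20 loss relative to this | logMAR |
|---|---|---|---|
| 20/20 | 1.0 × 0.2057 = 0.206 | 1 | 0.100 |
| 20/40 | 0.5 × 0.2057 = 0.103 | 2.0 | 0.100 |
| 20/100 | 0.2 × 0.2057 = 0.041 | 5.0 | 0.100 |

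**One line, if the chart is irregular (assumption: 20/70, 20/100, 20/200 at the poor end).** The step from 20/20 to 20/25 is 1.0 − 0.8 = 0.20. From 20/40 to 20/50 it is 0.5 − 0.4 = 0.10, again a ratio of 2. The steps either side of 20/100 are 20/70 − 20/100 = 0.086 and 20/100 − 20/200 = 0.10, so the ratio there is 2.0 to 2.3 instead of 5.

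**A mean that shows change where there is none (0.1-log lines).** One eye loses a line from 20/20: −0.2057. Another gains a line from 20/100: 0.2 × (10^0.1 − 1) = +0.0518. The mean decimal change is (−0.2057 + 0.0518)/2 = −0.077; the mean change in lines is zero.

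**Against the adverse event threshold (0.1-log lines).** Two lines are 1 − 10^(−0.2) = 0.369 decimal at 20/20 but 0.2 × 0.369 = 0.074 at 20/100.

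**Power, illustrative.** Only the 39 per arm comes from the plan (section 10.2.2, before the allowance for losses). Assumed: a two-arm t-test at 0.05 two-sided, one independent value per subject, mean loss 0.05 logMAR in one arm, and SD of the test-retest change 0.08 logMAR. On logMAR the standardised effect is 0.05 / (0.08 × √(2/39)) = 2.76, and simulated power is about 78%. For the decimal, baseline logMAR was drawn from a normal distribution with mean 0 to 0.2, either unlimited or limited to about −0.1 to 0.9:

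| Baseline SD (logMAR) | Power on decimal |
|---|---|
| 0.05 | about 76–77% |
| 0.1 | about 74–76% |
| 0.2 | about 68–73% |
| 0.3 | about 57–72% |

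The loss runs from about 1 point to about 20 points, depending almost wholly on a baseline spread that the documents do not give.

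**The case against.** The strongest reply is that this hardly matters in this population. The trial enrols mild to moderate dry eye, measures corrected acuity, and excludes glaucoma, sight-threatening retinal disease, corneal ulcers and several keratopathies. Most eyes may be near 20/20, where the weights differ little: 1.25 between 20/20 and 20/25, and 2 between 20/20 and 20/40. That stands as a limit on size.

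Three stronger readings are tempting, and the documents do not support them.

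- That the factor of five is a property of this trial. It assumes equal 0.1-log lines, and the chart's lines are never listed.
- That baseline acuity must be widely spread because only 20/200 or worse is excluded. An entry limit is not a distribution.
- That losses at poor acuity go unseen. Any loss of more than two lines is an adverse event at every starting acuity, and adverse event incidence is the primary safety outcome.

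It is also fair to say that on an irregular chart logMAR would not match the line count exactly, since adjacent lines there differ by about 0.08 to 0.30 logMAR. Conversion removes the dependence of a proportional loss on baseline acuity; it does not make logMAR and chart lines identical. Finally, the power figures model two arms, whereas the plan compares three by ANOVA and plans no power for BCVA. They show direction and order of size only.

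None of this defends the decimal as the scale for a mean.

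**Conclusion.** The point holds as a modest improvement to one secondary safety analysis. That a proportional loss is weighted by baseline acuity follows from the plan's own definition of the decimal and needs no assumption. The weight of one line at 20/20 is 2 times that at 20/40 on either chart considered, and 5 or about 2 times that at 20/100, depending on the chart assumed. The cost in power is small if most eyes are near 20/20 and could be material if baseline acuity varies widely; the documents cannot settle which.

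A reader might infer that the trial would miss a visual safety signal. The documents do not support that: the adverse event rule works in lines and is untouched. The primary OSDI analysis and the sample size do not involve BCVA. Nothing is lost in data capture either, because recorded decimals can be converted at any time.

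**What to change.** In Table 3 and section 10.1.2, state that each eye's recorded decimal is converted to logMAR, −log10(decimal), before changes, means, SDs, ANOVA or t-tests are computed, and that an increase in logMAR is a loss of acuity. Because −log10 is undefined at zero, say how an acuity too poor for the chart would be coded. Keep recording Snellen at the site, and leave the line-based adverse event rule as it is. Reporting the number of eyes by lines changed alongside the means would let readers relate the two.

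The cost is a sentence in the plan and one line of code. No new data, visit or site procedure is needed. It should be fixed before analysis so that the scale is not chosen after the results are seen.

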7.4.5.9 Intraocular pressure

Intraocular pressure (IOP) is a measurement through tonometry, based mostly on the force required to flatten the cornea, or the degree of corneal indentation produced by a fixed force. Goldman tonometry is based on the Imbert-Fick principle. [53]

The tonometry will be performed, after instillation of the topical anesthetic, with fluorescein and the use of the cobalt blue filter (after the evaluation of the surface staining). 2 samples will be taken and the average will be calculated, which will be recorded in the clinical file. The average will be recorded in the eCRF.

Management as AE: intraocular pressure equal to or greater than 22 mm Hg should be reported and managed as AE.

7.4.6 Study visits and activity programs

7.4.6.1 Description of activities per visit

The procedures are listed in the order in which they are suggested, trying to maintain the coherence of the evaluations and as far as possible, from the least invasive to the most invasive

7.4.6.2 Basal Visit

- Signature of the CRF: refers to the signing of the written informed consent document. Without obtaining informed consent, it is not possible to perform any of the study procedures
- Clinical history: refers to the technical, clinical, and legal document in which the subject's health conditions, medical acts, and other procedures performed on the subject are chronologically recorded. It includes anthropometric measurements, anamnesis, comprehensive ophthalmological examination that allows discerning the patient's eligibility, that is, evaluation of both eyes of ocular adnexa, slit lamp examination of the ocular surface and anterior segment and funduscopy. If the subject is taken from the established population base of the study center, the existing medical history may be used, and only an update must be made.
- Evaluation of concomitant medications: refers to the interrogation by the PI of the subject, inquiring about the use of medications.
- Urine pregnancy test: This refers to performing a rapid pregnancy test on all women of childbearing potential who wish to enter the study. By fertile age we mean women who have had their menarche and have not presented their menopause. Menopause is defined as 12 months from the last menstruation in women over 40 years of age, or who have had a hysterectomy or bilateral oophorectomy. Women of childbearing potential with contraceptive methods including bilateral tubal obstruction should be tested for pregnancy. This test will be performed by the PI or designated team person in accordance with the instructions on the device provided by the sponsor
- Vital signs: refers to the measurement of heart rate, respiratory rate, systemic blood pressure and temperature. This information must be contained in the patient's medical history and the evolution notes of the patient's clinical file.

- BCVA: See 7.4.5.8
- OSDI: See 7.4.5.1
- TFRT: See 7.4.5.2
- Ocular Surface Staining See 7.4.5.3 and 7.4.5.4
- Ophthalmologic evaluation: refers to the evaluation of the subject's ophthalmic structures, eyelids and adnexa, ocular surface, anterior segment, and posterior segment; not considered within the outcome variables. This evaluation is intended to identify alterations that may interfere with the course of the investigation or identify AEs. This examination will be recorded in the clinical file, in the CRF only what is considered an AE will be reported.
- IOP: See 7.4.5.9
- Eligibility criteria: refers to the review by the PI, where it is found that the subject can be included in the study by meeting the inclusion criteria and not meeting the exclusion criteria. See 5.1
- IP Assignment: This refers to determining the intervention that the patient will follow during the study. It will be carried out in accordance with section 7.3. This assignment will be made at the basal visit (day 1).

- Delivery of the IP and initiation of intervention: This refers to the delivery of the IP to the study patient, by the research center.
- AE Evaluation: Ver 7.4.5.7
- Delivery of patient material and filling instructions: This refers to the delivery by the PI to the subject of the subject's diary, identification card and calendar improving adherence. The assigned personnel will carry out prior training on the subject, on the filling of the diary.

7.4.6.3 Follow-up visit

- Concomitant Drug Evaluation: See 7.4.6.2
- Vital Signs: See 7.4.6.2
- BCVA: See 7.4.5.8
- Tear Film Rupture Time: See 7.4.5.2
- Ocular Surface Staining: See 7.4.5.3 and 7.4.5.4
- Comprehensive ophthalmologic evaluation: See 7.4.6.2
- IOP: 7.4.5.9
- AE Evaluation: Ver 7.4.5.7
- Adherence assessment: Adherence will be assessed in two ways, one through the initial vs. final weight of the medication bottle and the other through the record of applications in the subject's diary, adherence will be calculated. Adherence will be calculated based on the dosage of 2, 4 and 6 applications per day.

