6.1 Administered product

1. Investigational product

- Generic name: Sodium hyaluronate.
- Distinctive name: Multi-doses Lagricel® Ofteno.
- Active ingredients: Sodium hyaluronate 0.4%.

- 
- Pharmaceutical form: Ophthalmic solution.
 - Presentation: Multi-dose dropper bottle.
 - Prepared by: Laboratorios Sophia, S.A. de C.V.
 - Solution Description: Transparent solution, free of visible particles.
 - Packaging description: White bottle with a capacity of 10 mL, made of low-density polyethylene.

2. Dose of the investigational medicinal product

Three different dosages will be used, each of the groups will use one of the following:

- One drop BID, OU, for 30 days (suggested time between applications is 12 hours).
- One drop QID, OU, for 30 days (minimum time between applications of 3 hours).
- One drop 6x/D, OU, for 30 days (minimum time between applications of 3 hours).

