6.4 Procedure for monitoring and measuring adherence

For more than four decades, research has been conducted on the appropriate way to measure and quantify medication adherence, but none is considered the gold standard in both cross-sectional and longitudinal studies. [40, 41, 42, 43, 44, 45, 46, 47] There are different procedures to measure adherence to pharmacological interventions. The most common procedure is self-reporting, which includes: patient interviews, questionnaires and self-monitoring diaries. Its strengths are speed, flexibility, low cost and ease of implementation; They have a high degree of specificity for non-adherence, but the sensitivity and reliability for adherence is low. [47, 48] The biochemical measurement of the drug, or its metabolite, are methods that better confirm the use of the drug; but it raises costs, is impractical and of little use in ophthalmic applications, since concentrations at the peripheral level could be undetectable; samples of other tissues involve more invasive methods that would not be advisable. [47]

Medication counting is another way to measure adherence. Classically referred to as "pill counting," in ophthalmology it translates to the weight of the bottle. This is a simple, inexpensive, and non-invasive method.

The main disadvantages of this method are:

1. The application of the medication cannot be confirmed (it may have been intentionally pulled or instilled outside the eye)
2. It depends on the subject bringing back the medication. [47, 48]

However, in this study, the initial and final weight of the bottle will also be taken into account to measure adherence, at the same time adherence will be measured through the subject's diary.

A multi-procedure approach to measuring adherence is recommended. Because there is no measurement of ideal adherence, it is appropriate to use more than one method when trying to achieve results that resemble reality. Selecting two or more methods allows their strengths and weaknesses to be compensated, to capture adherence levels more accurately. [46]

The evaluation of adherence will be favored by means of the weight of the bottle and will be carried out in the following way, taking into account the following information: the weight of the drop, the initial weight of the container, the final weight of the container and the calculation of the total applications. The following simplified formula shall be used:

$$Ad = \frac{(P_i - P_f)100}{PT}$$

Where:

Ad = adherence

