P_i = weight of the container delivered to the subject at the beginning

P_f = weight of the container returned by the subject

PT = weight of the dosage indicated for the intervention

$$PT = (P_g)G$$

Where:

P_g = weight of one drop of the intervention, determined by the research and development department

G = number of applications indicated for the intervention

Packaging that does not retain its physical integrity will not be considered for the calculation of adherence. In cases where the container is not returned, or it has not preserved its physical integrity, adherence will be measured only through the subject's diary

Adherence through the subject's diary will be measured as follows:

$$Ad = (Ar)100/Ai$$

Ad = Adhesion

Ar = Registered Applications

Ai = Applications indicated for the products under investigation

There is no standardized parameter to define adequate adherence, it must be defined and delineated by the objectives of the particular research. [47]

For this study, a minimum adherence of 70% will be considered to be what is necessary to meet the objectives of the research both by subject diary and by bottle weight. Therefore, subjects who have an adherence of less than 70% will not be considered for the efficacy analysis, they will only enter the safety analysis.

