10.1.3 Procedure for handling missing data

Safety: The safety assessment will include in the analysis all those subjects (both eyes) who have been exposed at least once to the intervention, regardless of the visit in which they were eliminated from the study (ITT; *Intention To Treat* population).

Efficacy: Those subjects who meet a minimum adherence of 70% will be included in the statistical analysis to meet the objective of the study, taken from the weight of the IP. In cases where the container is not returned, or it has not preserved its physical integrity, adherence will be measured by means of the subject's diary.

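### The bottle-weight adherence formula counts one drop per application although each application is one drop in each eye, so 35% use of the indicated drops meets the 70% weight criterion

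*Combined protocol and SAP*

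**What the plan says.** Section 6.4 calculates adherence by weight as Ad = (Pi − Pf) × 100 / PT, where Pi and Pf are the bottle weights at delivery and return. It defines the denominator as "PT = weight of the dosage indicated for the intervention" and computes it as PT = Pg × G. Here Pg is the "weight of one drop of the intervention, determined by the research and development department", and "G = number of applications indicated for the intervention".

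Section 7.4.6.3 gives the daily count: "Adherence will be calculated based on the dosage of 2, 4 and 6 applications per day".

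Section 6.1 describes each regimen as one drop to both eyes; for the middle group it reads "One drop QID, OU, for 30 days (minimum time between applications of 3 hours". The BID group has a suggested interval of 12 hours between applications, and the 6x/D group a minimum of 3 hours.

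The result decides who is analysed for efficacy. Section 6.4 treats 70% as "necessary to meet the objectives of the research both by subject diary and by bottle weight", and subjects below it contribute to safety only. Section 10.1.5 likewise requires 70% on both measures for the per-protocol set. Section 10.1.3 differs: subjects reaching 70% are "included in the statistical analysis to meet the objective of the study, taken from the weight of the IP", and the diary is used only if the bottle is missing or damaged.

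**The concern.** The numerator is the weight lost from the whole bottle, so it includes the drops for both eyes. The denominator multiplies the weight of a single drop by a count of dosing times. With two drops per dosing time, the ratio is twice the share of the indicated drops that left the bottle.

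The 70% rule is the entry condition for the efficacy analysis, and 6.4 prefers bottle weight as the measure. The plan assigns the ITT population to safety and describes no ITT efficacy analysis that would serve as a check. A weight criterion that passes at half its nominal level lets under-dosed subjects into a comparison meant to identify the best dosing frequency.

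**Working it through.** The plan gives a threshold but no worked adherence value, so there is no figure of its own to reproduce. The check is direct arithmetic from its definitions.

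**Inputs**
- Dosing times per day, f = 2, 4, 6 (7.4.6.3)
- Treatment duration of 30 days (6.1)
- One drop in each eye, so 2 drops per dosing time (6.1; the abbreviation list defines OU as both eyes)
- PT = Pg × G, with Pg the weight of one drop (6.4)
- Threshold of 70% (6.4, 10.1.3, 10.1.5)

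**General result.** Let u be the share of indicated drops dispensed. The weight lost is u × 2 × f × 30 × Pg, and PT as written is f × 30 × Pg. Then

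Ad = 100 × (u × 2 × f × 30 × Pg) / (f × 30 × Pg) = 200u.

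Drop weight, frequency and number of days all cancel. The factor is exactly 2 in every arm, and no drop weight has to be assumed.

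**Over 30 days**

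| | BID | QID | 6x/D |
|---|---|---|---|
| Applications, G = f × 30 | 60 | 120 | 180 |
| Indicated drops, 2 × G | 120 | 240 | 360 |
| Ad at full use, 2G / G | 200% | 200% | 200% |
| Ad at full one-eye use, G / G | 100% | 100% | 100% |
| Drops that meet 70% as written, 0.70 × G | 42 | 84 | 126 |
| As share of indicated drops | 35% | 35% | 35% |
| Drops that should be needed, 0.70 × 2G | 84 | 168 | 252 |

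The boundary is sharp: u = 35% gives Ad = 70.0% and passes, while u = 34.9% gives 69.8% and fails. Use from 35% to just under 70% is wrongly passed by weight.

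**Overlap between arms.** As written, a 6x/D subject passes by weight with 126 drops, close to a complete BID course (120). At the intended cut-off of 252 drops, that subject would have used more than a complete QID course (240).

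**Effect under each inclusion rule**
- *Weight decides (10.1.3).* A subject at 35% use enters the efficacy analysis.
- *Weight and diary both required (6.4, 10.1.5).* The diary ratio is registered over indicated applications. It is not doubled if both are counted as dosing times. A subject at 35% use in both eyes has 21, 42 or 63 true applications and passes only if the diary records at least 42, 84 or 126.
- *One-eye dosing, diary counting dosing times.* A subject treating one eye at 70% of dosing times uses 42, 84 or 126 drops. For BID, weight gives 42/60 = 70%, an accurate diary gives 42/60 = 70%, and the share of indicated drops is 42/120 = 35%. The same percentages hold in the other arms. This subject passes under either rule.

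**The case against.** The strongest reply is that the protocol never defines an application. Section 6.4 describes PT as the weight of the indicated dosage, which is for both eyes, so an analyst working from that description might count both eyes anyway. The intervals in 6.1 could also be read as the time between drops to the same eye. But a per-eye count would need 4, 8 and 12 applications a day, whereas 7.4.6.3 states 2, 4 and 6 and no section adds a factor for two eyes. The description of PT and the formula for PT therefore disagree, and the formula is what would be programmed.

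Other points stand in part:
- The diary form is not in the documents. If each eye were logged separately against 2, 4 and 6 a day, the diary ratio would be doubled too. The contrast between the two measures and the one-eye case both assume that the diary counts dosing times.
- Where weight and diary are both required, an accurate diary of dosing times still excludes a subject at 35% use in both eyes. What is lost is the cross-check on inaccurate diaries. Section 6.4 says of self-report methods, "They have a high degree of specificity for non-adherence, but the sensitivity and reliability for adherence is low", and it uses two methods so that each offsets the other's weakness.
- Values near 200% in adherent subjects would probably be noticed, and PT can be recalculated from the recorded weights. That makes the error cheap to repair, but the plan states no upper limit that would flag it.
- Bottle weight shows drops dispensed, not drops that reached the eye, as 6.4 acknowledges. The 35% is a share of indicated drops dispensed.
- The final-visit section refers to itself for the adherence method, so using the 2, 4 and 6 count over the full 30 days is an inference. The factor of 2 does not depend on it, because the days cancel.

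**Conclusion.** The formula is wrong as written and should be fixed. Weight-based adherence computes at twice the share of indicated drops used, in all three arms, and the nominal 70% weight criterion is met at 35%. This rests only on the plan's own definitions, with an application read as a dosing time, as the 2, 4 and 6 daily count requires.

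The effect on the efficacy set depends on which inclusion rule governs, and the sections disagree. It is direct under 10.1.3 and partial under 6.4 and 10.1.5. The formula error is the same in every arm, so the formula does not itself favour one arm. The number of subjects wrongly included cannot be estimated from the documents.

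**What to change.** 1. In 6.4, set PT = Pg × 2 × G, which is 120, 240 and 360 drops over 30 days. At V1, use the number for the days elapsed; for example, 14 full dosing days give 28, 56 and 84 applications, or 56, 112 and 168 drops.
2. In 6.4, state that one application is one dosing time covering both eyes. In 7.4.6.3, state that the weight calculation counts both eyes, and correct the final-visit cross-reference to point there.
3. Keep the diary formula in applications, and say whether a diary entry confirms that both eyes were treated.
4. Reconcile 6.4, 10.1.3 and 10.1.5 on whether weight alone, or weight and diary together, define the efficacy set.

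The cost is a one-line formula change, short definitions and one reconciled sentence on the analysis set. Dosing and the 70% threshold stay as they are. Some subjects may newly fall below 70% by weight, as the criterion intends. Section 10.2.2 adds 8 subjects per group (39 raised to 47) for possible losses, but 10.1.4 describes the 20% loss as loss to follow-up or withdrawal of consent. The sponsor should state whether exclusions for low adherence are meant to come out of that allowance.
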